**PROJECT DESCRIPTION**

In addition to the Application and the Abstract, briefly describe the research project using the numbered headings below. Give sufficient detail for each of the following points to facilitate local review. Use "none" or "NA" if appropriate. *NOTE: This description is for local review committees only and does not need to have the same technical detail as the narrative portion of an application for funding submitted for outside review. However, the description of involvement of human subjects must not differ in substance from the relevant application.*

**2. Purpose:**

The proposed trial will use a double-blind, placebo-controlled design to conduct the first randomized controlled trial of the COMT inhibitor, tolcapone, in nicotine dependent women.

**Aim #1.** To determine if tolcapone is superior to placebo in attenuating the severity of nicotine withdrawal and smoking urges during short-term abstinence. Withdrawal severity will be assessed by a self-report scale and cognitive assessment, including a sustained-attention task. Smoking urges will be assessed by a self-report scale.

*Hypothesis #1:* Tolcapone will be superior to placebo in reducing the severity of withdrawal and smoking urges during short-term abstinence.

**Aim #2.** To determine if tolcapone is superior to placebo in reducing smoking self-administration in a human laboratory model (Smoking Choice Paradigm) and reducing subjective ratings of smoking reinforcement.

*Hypothesis #2A:* In the smoking choice paradigm following short-term abstinence, the group receiving tolcapone will choose fewer cigarette puffs than the group receiving placebo.

*Hypothesis #2B:* In the smoking choice paradigm following short-term abstinence, the group receiving tolcapone will rate smoking as less reinforcing than the group receiving placebo.

**3. Background:**

Existing smoking cessation pharmacotherapies may be less effective in women than men (Cepeda-Benito *et al*, 2004), which may contribute to poorer quit rates in women (Perkins, 2009). Women may also have higher risks of tobacco-related morbidity and mortality than men smokers(USDHHS, 2001, 2004). Thus, there is a great need for treatments tailored for women smokers.

There are several reasons why the inhibition of the catechol-O-methyltransferase (COMT) enzyme may be a promising smoking cessation pharmacotherapy in women.

## COMT Inhibition as a Novel Treatment for Nicotine Addiction in Women

*i) High COMT enzyme activity is implicated in risk for nicotine dependence and poor smoking cessation outcomes.* Individuals with the high COMT enzyme activity allele (Val), are more likely to smoke (Enoch *et al*, 2006; Shiels *et al*, 2008), have higher risk for nicotine dependence (Tammimaki and Mannisto, 2010), experience more withdrawal symptoms (Loughead *et al*, 2009) and smoking urges (Wang *et al*, 2008) during nicotine-abstinence, have poorer smoking cessation outcomes (Colilla *et al*, 2005), and have diminished therapeutic effects of nicotine replacement therapy for smoking cessation (Johnstone *et al*, 2007), relative to those with the allele that inhibits COMT enzyme activity (Met).

*ii) There are several biologically plausible mechanisms by which COMT enzyme inhibition could counter nicotine dependence.* COMT enzyme is abundant in the brain and affects prefrontal cortical (PFC) and striatal dopaminergic systems implicated in nicotine dependence.

The COMT enzyme metabolizes dopamine (DA) (Tammimaki *et al*, 2010). A functional variant of the gene which codes for the COMT enzyme, reduces enzymatic activity (i.e., Met relative Val allele carriers) (Chen *et al*, 2004) results in higher basal DA levels, primarily in the prefrontal cortex, but also in the striatum (Gogos *et al*, 1998; Tammimaki *et al*, 2010; Yavich *et al*, 2007) and lower nicotine-induced DA release in ventral striatal regions (Brody *et al*, 2006). Nicotine-induced striatal DA release increases nicotine's reinforcing and hedonic properties (Barrett *et al*, 2004) and alleviates abstinence-related smoking urges (Brody *et al*, 2004) and mood disturbances (Brody *et al*, 2009). So, the fact that COMT enzyme inhibition reduces nicotine-induced striatal DA release suggests it may also reduce nicotine's reinforcing properties, which should reduce smoking maintenance. Smoking abstinence normally results in reduced basal DA levels in the ventral striatum, which is associated with withdrawal symptoms (Zhang *et al*, 2012). Since inhibition of the COMT enzyme increases basal striatal DA levels, it should diminish abstinence-related withdrawal symptoms. This is important because withdrawal symptoms (e.g., irritability, negative affect) and smoking urges increase relapse-risk during smoking cessation attempts (Allen *et al*, 2009a; Allen *et al*, 2009b; Allen *et al*, 2008b). PFC DA levels influence cognitive function. Abstinence-related cognitive decrements are a core feature of withdrawal (Hughes, 2007) and increase smoking relapse risk (Patterson *et al*, 2010) (de Wit, 2009). As such, cognition has been proposed as a treatment target for smoking cessation (Sofuoglu *et al*, 2013). High COMT enzyme activity is associated with poor performance on cognitive functions implicated in relapse risk (e.g. working memory, sustained attention (Barnett *et al*, 2007; Egan *et al*, 2001) (Diaz-Asper *et al*, 2008; Dumontheil *et al*, 2011; Loughead *et al*, 2009)) and with greater nicotine-abstinence related cognitive decrements (Herman and Sofuoglu, 2010; Loughead *et al*, 2009). Therefore, since COMT enzyme inhibition increases PFC DA levels, it is expected to diminish abstinence-related cognitive decrements, which could reduce relapse-risk since abstinence-related cognitive decrements increase smoking relapse.

*iii) Many of the effects of COMT enzyme inhibition may be sex-sensitive.* Inhibition of COMT enzyme activity has sex-sensitive effects on psychiatric risk factors (Tunbridge and Harrison, 2010). Such sex-sensitive effects may arise from neurobiological sex differences in DA systems which are regulated by the COMT enzyme (drug-stimulated striatal DA release (Munro *et al*, 2006) and basal striatal DA levels (Laakso *et al*, 2002)); gonadal hormones' modulation of DA (e.g. estradiol's DA agonist-like effects (Becker, 1990a, b, 2000; Becker and Hu, 2008; Pasqualini *et al*, 1995; Thompson and Moss, 1994; Xiao and Becker, 1994)); or gonadal hormone's modulation by COMT (COMT enzyme's catabolism of estrogens (Tunbridge *et al*, 2010)).

For example, COMT enzyme activity's effects on nicotine-abstinence related cognitive decrements are sex-sensitive and moderated by menstrual cycle phase (Jacobs and D'Esposito, 2011). Nicotine withdrawal symptoms and smoking urges may be stronger in women (al'Absi *et al*, 2002; Leventhal *et al*, 2007), symptoms of anxiety and depression are more strongly linked with nicotine withdrawal and smoking relapse in women (Weinberger *et al*, 2009) and high COMT enzyme activity has been more strongly linked with depression, anxiety and related phenotypes in women than men (Baune *et al*, 2008; Domschke *et al*, 2012; Domschke and Dannlowski, 2010; Domschke *et al*, 2007; Domschke *et al*, 2004; Eley *et al*, 2003; Enoch *et al*, 2003; Funke *et al*, 2005; Hamilton *et al*, 2002; Hettema *et al*, 2008; Kempton *et al*, 2009; Kim *et al*, 2006a; Lonsdorf *et al*, 2010; Massat *et al*, 2005; Olsson *et al*, 2005; Opmeer *et al*, 2010; Rothe *et al*, 2006; Stein *et al*, 2005; Weiss *et al*, 2007; Williams *et al*, 2010).

*iv) Our preliminary data support our hypotheses in women smokers.* We recently demonstrated that overnight-abstinent women smokers with high COMT enzyme activity reported greater severity of certain withdrawal symptoms (e.g., difficulty concentrating) than Met carrier women or men with high or low COMT enzyme activity (Herman *et al*, 2013). Our preliminary data extend these findings in a larger sample to show that in women, but not in men, high COMT enzyme activity is associated with more severe withdrawal, smoking urges and worse cognitive function following overnight abstinence. Additionally, high COMT enzyme activity women rated their anxiety higher during placebo yet reported greater alleviation of anxiety symptoms with nicotine administration. As such, inhibition of COMT enzyme activity would be expected to ameliorate withdrawal symptoms (including negative mood) and smoking urges, particularly in women, providing another mechanism by which this intervention would be expected to improve smoking cessation outcomes in women.

*v) Approved medications that inhibit COMT enzyme activity are available for clinical use.* COMT enzyme activity can be pharmacologically inhibited with tolcapone, which crosses the blood-brain barrier and inhibits COMT enzyme activity in the brain (Ceravolo *et al*, 2002) to a similar degree as the genetic variant described above (i.e., Met allele; 25% reduction (Apud *et al*, 2007)). While it is approved as an adjunct to DA treatments in Parkinson's disease (Haasio, 2010), tolcapone has been shown to improve aspects of cognitive function in healthy individuals (Apud *et al*, 2007) and patients with Parkinson's disease (Gasparini *et al*, 1997) or Pathological Gambling (Grant *et al*, 2013) and in pre-clinical studies (Liljequist *et al*, 1997; Tunbridge *et al*, 2004). Tolcapone reduced gambling urges and behaviors (Grant *et al*, 2013) and another COMT inhibitor (entacapone) diminished cannabis-craving in dependent individuals (Shafa *et al*, 2009). Taken together, these findings support tolcapone's safety and efficacy in improving symptoms implicated in addiction risk, including cognitive performance and craving in other addicted populations.

#### **4. Significance:**

Nicotine dependence has been a persistent public health problem and identifying effective medications for the treatment remains a high priority. Women smokers, compared to men, have lower smoking quit rates (Perkins, 2009), may find smoking cessation medications to be less effective (Cepeda-Benito *et al*, 2004), and may have higher risks of tobacco-related morbidity and mortality (USDHHS, 2001, 2004). Thus, there is a great need for treatments tailored for women smokers. The results will provide important evidence that COMT inhibition is a viable therapeutic target for smoking cessation in women, and contribute to a better understanding of its potential mechanisms of action.

## 5. Research Plan:

### A. Overview

The proposed study will assess the effects of the COMT inhibitor, tolcapone, versus placebo on reducing withdrawal symptoms (including cognitive decrements), smoking urges and smoking behavior, in women smokers. This will be a double-blind, placebo-controlled study, with 60 women smokers. After completing an *ad libitum* smoking baseline, participants will be randomized to 8-days of the COMT inhibitor tolcapone (100mg three times a day (TID) for 7 days then 100mg once on day 8) or placebo (Apud *et al*, 2007; Grant *et al*, 2013). For the first two days of the medication period, participants will continue to smoke *ad libitum* and attend brief check-in sessions once daily to take one dose and be given the remaining two doses to take at home. On medication days 3-5, they will be given take-home doses and will be asked to check in daily by phone or in person and continue to smoke *ad libitum*. On the evening of medication day 5, the 60-hr (2 ½ day) abstinence period will begin. During the 2 ½ day abstinence period, participants will attend brief check-ins daily, to receive their dose (plus take-home doses) and to be screened for abstinence adherence (breath CO levels; urine cotinine). Measures of withdrawal and smoking urges will be collected at all sessions. On Medication Day 8, a test session will be conducted where assessment of cognitive function and smoking behavior will be collected. At the conclusion of the session on Medication Day 8, subjects will be stop the medication. A brief follow-up session will be completed approximately 1-week after the final medication day then subjects will be discharged from the study. A between-subject design will be used since the study involves numerous visits and several days of abstinence and we predict that a within-subject design would be overly burdensome to participants and result in high attrition rates. A between-subject design also avoids possible medication carryover effects.

**Subjects:** Women smokers, aged 18-45, who are able to read and write English and are in good health (as verified by medical history, screening examination, and screening laboratory tests) will be included. Smoking status will be determined by self-reported history of smoking daily for the past 12 months,  $\geq 5$  cigarettes daily, , a urine cotinine of at least 3 (out of 6) as measured by the NicAlert dipstick method to measure smoking status. Subjects will be excluded if they are using other psychotropic medications, have contraindications to tolcapone use based on medical history (including allergy to tolcapone, lifetime history of diagnoses associated with liver disease (e.g., alcohol dependence, hepatitis), renal impairment, history of nontraumatic rhabdomyolysis or hyperpyrexia and confusion possibly related to a medication or lifetime history of syncope), screening examination (e.g., symptomatic orthostatic changes during screening), or screening laboratory tests (e.g., LFT $>2$  times greater than the upper limit of the normal range)) have other substance use disorders, are pregnant or breast-feeding or not using acceptable birth control methods, have current psychotic disorder, bipolar disorder, homicidal or suicidal ideation, have current (past month) substance use disorder, other than nicotine dependence, or are unable to fulfill the scheduled visits and procedures.

### B. Outcome Measures

COMT Inhibition as a Novel Treatment for Nicotine Addiction in Women

Table 1. Schedule of Assessments and Interventions	Time (min)	Screen	Ad Libitum Baseline	Brief Medication Visits Ivisit/day, 4 days	2 ½ day Abstinence End of Trial	1-week Follow-up
Screen & Baseline Measures & Smoking Behavior Measures						
Psychiatric and Medical Screen	35	X				
Demographics, Menstrual Cycle (MCAQ)	7		X			
Smoking History, Nicotine Dependence(FTND), urine cotinine dipstick	5	X				
Timeline Followback	5		X			X
Pill Administration, Abstinence Adherence and Physiological Measures						
Tolcapone or Placebo	2			X	X	
CO levels, Breathalyzer, urine cotinine	2	X	X	X	X	X
Urine toxicology	3	X	X	X (day 1)	X	
Urine pregnancy screen	3	X		X (day 1)	X	X
Vitals (HR, BP)	2	X	X	X	X	X
Blood Draws						
Genetics (rs4680)	3	X				
Labs for liver function	3	X			X	X
Nicotine, Cotinine, Hormones	3		X		X	
Self-report Measures of Withdrawal, Craving, Drug Effects, Mood and Impulsivity						
Withdrawal (MNWS); Smoking Urges(BQSU)	6		X	X	X	X
Subjective Nicotine Effect (DEQ)	2		X		X	
Adverse Drug Effects (AEF)	3			X	X	X
Depression (CES-D); Anxiety (STAI)	8		X		X	X
Affect (PANAS)	3		X	X	X	X
Impulsivity (BIS-II, BIS/BAS)	7		X			
Cognitive Tasks						
IQ	10	X				
Memory; Learning (digit span, HVLT)	25		X		X	
Sustained Attention (RVP, CPT)	10		X		X	
Cognitive Flexibility (CGT, SOC, Stroop))	10		X		X	
Laboratory Smoking Behavior						
Smoking Choice Paradigm	90				X	
TOTAL ESTIMATED TIME (hours):		1	1 ¾	1 ½ (20min/visit)	3	½

### *Subjective/Questionnaires*

Mini International Neuropsychiatric Interview (M.I.N.I.): At screening, Axis I psychiatric disorders will be assessed with the Mini International Neuropsychiatric Interview (M.I.N.I.) (Sheehan *et al*, 1998) plus questions for classification by new DSM-V as well as DSM-IV criteria. This assessment will be administered once only at initial screening and will be used to help determine eligibility of the subject to participate in the trial.

Fagerstrom Test of Nicotine Dependence (FTND): This self-report measure FTND (Heatherton *et al*, 1991) will assess degree of nicotine dependence. It will be administered at screening.

Barrett Impulsivity Scale (BIS-11): This self-report measure assesses facets of impulsivity and is designed to measure impulsivity as a 'trait' (Patton *et al*, 1995). The questionnaire is composed of 30 items scored from 1 (rarely/never) to 4 (almost always/always). Impulsivity has been proposed to relate to the development and maintenance of addictive behaviors (de Wit, 2009; Krishnan-Sarin *et al*, 2007; Moeller *et al*, 2001). It will be administered at *ad libitum* baseline.

Behavioral Inhibition/Activation Scale (BIS/BAS): This self-report measure consists of 20 items, scored from 1 (strongly disagree) to 4 (strongly agree) and assesses 'behavioral inhibition' (i.e., anticipation of punishment) and 'behavioral activation' subscales (i.e., reward responsiveness, drive, fun-seeking) (Carver and White, 1994). These traits have been linked with impulsive behaviors and with the development and maintenance of addictive behaviors (de Wit, 2009; Krishnan-Sarin *et al*, 2007; Moeller *et al*, 2001). It will be administered at *ad libitum* baseline.

Menstrual Cycle Assessment (MCAQ): This questionnaire will be administered at *ad libitum* baseline and asks about use of contraception, including hormonal contraception, date of last period, frequency and regularity of cycles and symptoms of menopause or peri-menopause.

Demographics, smoking history: At screening, subjects will also be asked about self-described race and ethnicity as well as years of smoking, age of onset, and past cessation attempts and use of other nicotine products (e.g., e-cigarettes).

Minnesota Nicotine Withdrawal Symptom Checklist (MNWS): At all sessions except screening, smokers will be asked to rate nicotine withdrawal symptoms (cigarette craving, irritability/anger, anxiety/tension, difficulty concentrating, restlessness, increased appetite, depressed mood, and insomnia) on a 100 mm scale, "not at all" to "extremely" (Hughes and Hatsukami, 1986).

Brief Questionnaire on Smoking Urges (BQSU): This 10-item scale reliably measures cigarette craving (Tiffany and Drobes, 1991) and will be administered at all sessions except screening.

Positive and Negative Affect Schedule (PANAS): The PANAS is a 20-item scale that assesses both negative and positive affective states (Watson *et al*, 1988). This scale is sensitive to the affective symptoms of tobacco withdrawal and predicts relapse to smoking (Kenford *et al*, 2002) and will be administered at all sessions except screening.

Premenstrual Assessment Form (PAF): Given their potential overlap with withdrawal symptoms (Allen *et al*, 1996; Allen *et al*, 1999; Carpenter *et al*, 2006), premenstrual symptoms will be assessed with the 10-item PAF (Halbreich *et al*, 1982) at all sessions except screening so they can be used as covariate in analyses focusing on withdrawal symptoms.

Drug Effects Questionnaire (DEQ): Smokers will rate 10 items that are related to nicotine effect on a 100 mm scale, "not at all" to "extremely." The items are feeling "stimulated", "high", "anxious", "sedated", "down", "good drug effects", "bad effects", "drug strength" as well as

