Plasma cotinine, 3-hydroxycotinine (3-HC), and nicotine levels: Plasma samples will be taken at the *ad libitum* smoking baseline session and at the post-abstinence final session. 3-HC is the main metabolite of cotinine and the ratio of 3-HC/cotinine, also known as the nicotine metabolite ratio, reflecting the rate of nicotine clearance. Smokers with high 3-HC/cotinine ratio (faster metabolizers) reported greater craving for cigarettes following overnight abstinence and greater nicotine-induced subjective drug effects, suggesting the 3-HC/cotinine ratio may influence the reinforcing effects from nicotine or experience of abstinence. Plasma nicotine levels will also be measured at baseline to confirm smoking status and at the post- abstinence session to confirm abstinence. Assays for nicotine, cotinine, and 3-HC levels will be performed in [name] laboratory. Briefly, nicotine, cotinine and 3-HC are measured using HPLC coupled to tandem mass spectrometry (LC/MS/MS) employing stable isotope labeled internal standards as previously described.

Alveolar carbon monoxide: A measure of expired CO levels will be taken at the beginning of each visit and during the Smoking Choice Paradigm. At the medication stabilization *ad libitum* check-in sessions, CO readings will be collected as a secondary measure of smoking levels. During the check-in sessions and final session during the abstinence period, CO readings  $\leq 8$ ppm will be used to verify compliance with smoking abstinence on the first morning check-in following overnight abstinence. This level was recommended by the SRNT Subcommittee on

Biochemical Verification to confirm overnight abstinence (Benowitz et al. 2002). At subsequent abstinence check-ins (across the 60 hr abstinence) the subject will be considered to have met the criteria for abstinence-related bonus payment if their CO is  $\leq 8$ ppm and has not increased since their prior abstinence visit.

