## E. Study Procedures

Subjects will be asked to refrain from consuming alcoholic beverages and drugs during study participation, which will be verified by a urine drug quick test and breathalyzer. If results indicate non-compliance with these study procedures, subjects will be discharged from the study. Subjects will be instructed to drink their typical amount of caffeinated beverages in the morning to minimize caffeine withdrawal, which could confound the study measures. For outline of protocol per session and estimated timings, see Table 1. Briefly, sessions will include:

In person Screening Session: This session will involve: a) obtaining informed consent; b) smoking history and assessment of nicotine dependence severity based on FTND; c) CO levels will be measured ; d) urine cotinine of 3 (out of 6) or higher on the semi-quantitative cotinine dipstick will be measured to ensure smoking status and a urine sample will be collected for quantitative cotinine assay; e) screening for co-morbid psychiatry conditions using the MINI; f) physical examination including ECG and vitals; g) urine analysis for drug screening and urine pregnancy test; h) ) blood draws for: 1.) laboratory examination including CBC, ALT, AST, alkaline phosphatase, glucose, BUN, creatinine and 2.) DNA; i) SILS to measure estimated IQ.

Ad libitum Smoking Session: Those found eligible will complete the *ad libitum* smoking baseline assessment, consisting of self-report measures of mood, withdrawal and smoking urges, cognitive tasks and vitals. Biochemical measures will include CO levels, breathalyzer, urine toxicology for drug screening, urine cotinine, blood draws for: 1.) nicotine and nicotine metabolite levels and 2.) gonadal hormone levels (progesterone, estradiol).

Medication Initiation (Medication Days 1-2) and Abstinence Phase (Medication Days 6-7) Sessions: Those subjects who were found eligible will be randomized to medication

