## COMT Inhibition as a Novel Treatment for Nicotine Addiction in Women

(tolcapone) or placebo, in a double-blind fashion. Urn randomization will endeavor to balance medication and placebo groups for race, baseline smoking rate, and menstrual cycle phase. Although genotype will not be known for all subjects prior to randomization, in cases when it is known (e.g., genetics sample collected at baseline is processed prior to randomization) will be counterbalanced for genotype as much as possible.

Brief once-daily visits during the medication initiation (Medication Days 1-2) and abstinence periods (Medication Days 6-7) will serve four purposes: 1) administer pill in person and give take-home doses with instructions (100mg three times a day (TID); subjects will be asked to self-administer the take-home doses at approximately 6-hour intervals); 2) screen for adverse medication effects (Adverse Events Form; heart rate and blood pressure); 3) check for nicotine abstinence compliance (expired CO; urine cotinine; self-reported cigarettes per day); 4) collect self-report measures of withdrawal, smoking urges and mood, which are hypothesized to fluctuate with abstinence and/or medication.

Medication Initiation and Stabilization Phase (Medication Days 1-5): For the first five days of medication, subjects will be told they may smoke their cigarettes as much as they choose (*ad libitum*). They will be asked to attend one brief session per day on Medication Days 1-2. These first days will allow the participants to achieve medication optimal dosing and steady state levels prior to initiating the abstinence period. For Medication Days 3-5, the subjects will maintain the same dose and take the doses at home. During these days, they will have either in person/or phone check-in with a member of the research team to check for reported adverse effects. Brief questions about smoking (e.g., cigarettes per day) and whether they noticed changes in mood or smoking urges will also be asked. These phone check-in days are designed to maintain contact to continue monitoring for safety purposes, while reducing the burden on the participants. Subjects will have an emergency contact so they can access care if needed during this time.

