Abstinence Medication Maintenance Sessions (Medication Days 6-7): Beginning on the evening of Medication Day 5, subjects will be asked to refrain from smoking their cigarettes. They will be asked to attend one brief check-in session per day on Medication Days 6-7. Medication doses continue at 100mg TID during this phase. Smoking abstinence will be tracked with CO-levels, urine cotinine screens and self-report.

Post-2 ½ day Abstinence End of Trial Session (Medication Day 8): At the testing session, participants will have been abstinent from smoking for 2 ½ days or more (e.g., 8PM Medication Day 5 through 8AM Medication Day 8), and maintained on tolcapone (or placebo) for the previous week. Participants will take their final dose (100mg) on the morning of Medication Day 8 then complete the same self-report measures and cognitive tasks from the baseline *Ad libitum* Smoking session. Blood will be collected for assessment of nicotine and cotinine (as additional confirmation of abstinence), gonadal hormones and liver function tests (to screen for adverse effects of tolcapone).

Subjects will then complete the Smoking Choice Laboratory Procedure. As we have done in previous studies, participants will complete this paradigm in a designated, negative pressure room. After sample smoking (2 sec cigarette puffs separated by a 20 sec interval) to measure subjective responses to smoking following abstinence, participants exchange tokens for cigarette puffs (2 puffs) or money (\$0.75) every 9 minutes until 1.5 hours had elapsed (i.e., 9 min x 10

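### The abstinence check is meant to cover nicotine, but the instruction and self-report cover only cigarettes, and the nicotine biomarkers carry no threshold or analysis role

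*Protocol*

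**What the plan says.** **Screening and eligibility.** The smoking-history item in section 5.B of the protocol (Subjective/Questionnaires) asks about "past cessation attempts and use of other nicotine products (e.g., e-cigarettes". The Subjects paragraph of section 5.A gives the answer no consequence. The nearest exclusions are "Subjects will be excluded if they are using other psychotropic medications" and a rule for women who "have current (past month) substance use disorder, other than nicotine dependence". Neither names e-cigarettes or any other non-cigarette nicotine product.

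**Instruction.** Section 5.A states: "On the evening of medication day 5, the 60-hr (2 ½ day) abstinence period will begin". In section 5.E, from that evening, "subjects will be asked to refrain from smoking their cigarettes". The broader rule at the start of 5.E is "Subjects will be asked to refrain from consuming alcoholic beverages and drugs during study participation", verified by urine drug test and breathalyzer.

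**Checks.** Section 5.E gives one purpose of the brief visits as to "check for nicotine abstinence compliance (expired CO; urine cotinine; self-reported cigarettes per day". The Biochemical part of 5.B sets CO at 8 ppm or below for the first abstinence check-in. For later check-ins it makes the bonus payment depend on the same level, provided CO is at that level "and has not increased since their prior abstinence visit". Urine cotinine is taken at check-ins, and plasma nicotine and cotinine are drawn on Day 8 as confirmation of abstinence. None of these has a cut-off. The Individual Stopping Rules discharge women for missed abstinence tests, not for positive ones.

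**Analysis.** The SAP covariates are menstrual cycle phase, race and baseline smoking severity. No abstinence-based analysis is planned.

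**The concern.** All the main outcomes assume nicotine deprivation: withdrawal, smoking urges, sustained attention during abstinence, and puff choice after it. The protocol calls its target nicotine abstinence, but the parts that put the target into practice deal with smoking. The instruction is about cigarettes, the self-report item counts cigarettes, and the only numeric criterion is CO. It is general knowledge, not stated in the documents, that CO reflects smoke rather than nicotine from products without combustion.

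A woman who replaces cigarettes with an e-cigarette for the 60 hours would comply with the plan as written. Her withdrawal and urges would probably be blunted in either arm, which leaves less for tolcapone to improve. The main risk is therefore a diluted contrast, in a trial whose sample size has almost no spare power.

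**Working it through.** **1. Text side by side**

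| Element | Covers other nicotine products? | Rule attached? |
|---|---|---|
| Screening history (5.B) | Yes | None |
| Eligibility (5.A, Subjects) | Not named | None |
| Abstinence instruction (5.E) | No, cigarettes only | Refrain from Day 5 evening |
| Alcohol and drugs instruction (5.E) | Not named; women smoke freely through Day 5 under it | Discharge |
| Self-report at check-ins (5.E) | No, cigarettes per day | None |
| CO (5.B Biochemical; Payment) | No (general knowledge) | 8 ppm limit; bonus |
| Urine cotinine (5.B, 5.E) | Yes | None |
| Day 8 plasma nicotine and cotinine (5.B, 5.E) | Yes | None |

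The Timeline Follow-Back does not fill the gap. It covers the past week and is given at baseline and about one week after the final medication day, so its window largely misses Days 5 to 8.

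**2. The plan's own power figure**

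Inputs from the SAP: N=60, alpha=.05, f=.37, stated power 80%. The method is a noncentral F test with 1 numerator df, lambda = N × f², df2 = N − 2, and equal allocation assumed.

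- N=60, f=.37: lambda = 60 × .37² = 8.21; power 80.5% (80.3% to 80.4% with 3 to 5 covariates).
- N=52, f=.40: lambda = 52 × .40² = 8.32; power 80.7%.

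Both reproduce the SAP. The smallest f detectable with 80% power at N=60 is .368, so f=.37 leaves no margin.

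**3. Dilution**

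The documents give no share of women who would keep using nicotine, so the share q is an assumption. The worst case is that these women show no drug effect at all and the SD is unchanged: f becomes f × (1 − q).

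| q | f × (1 − q) | Power at N=60 | N for 80% power |
|---|---|---|---|
| 0 | .370 | 80.5% | 60 |
| 5% | .352 | 76.3% | 66 |
| 10% | .333 | 71.8% | 74 |
| 20% | .296 | 61.6% | 92 |

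Milder assumptions move up the table. If 20% use other products but only half continue, q = .20 × .5 = .10 and power is 71.8%. If those women also keep half the drug effect, the loss equals q = .05 and power is 76.3%.

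**4. What cotinine could show**

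Assume a half-life of 16 to 20 h (not in the documents). After 60 h of true abstinence the remaining fraction is 0.5^(60/16) = .074 to 0.5^(60/20) = .125, a fall of 8-fold to about 13.5-fold. Residual cotinine blurs a single reading without a cut-off. A within-woman fall from baseline is informative, and plasma cotinine is planned at both the *ad libitum* baseline and Day 8.

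**The case against.** The strongest reply is that the protocol already measures nicotine exposure. Urine cotinine is tracked at check-ins, and the Day 8 plasma sample is drawn expressly to confirm abstinence. A woman vaping steadily up to Day 8 would not show the expected fall in cotinine. This stands against any reading that such use is undetectable, or that the plan relies on CO alone. It does not supply the missing rule: nothing says what level counts as abstinent or what follows if a woman is not.

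Second, the gap is inferred from silence. Consent pages are not in the reviewed text, the project description says it need not carry full technical detail, and a site might treat nicotine replacement as a psychotropic medication. The screening item may also refer to past use. These points are fair, but the eligibility and procedure sections are where such a rule belongs, and e-cigarettes do not plausibly fall under the medication exclusion.

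Third, the power loss combines an assumed share of users, continued use throughout and zero drug effect. The last is doubtful for attention, since the Background says tolcapone improves aspects of cognition in healthy people. Also, f=.37 is a detectable effect, not an expected one. The SAP's genotype proxies, using f = √(F/df) with df=48, give √(16.9/48) = .59 for urges, √(9.9/48) = .45 for attention and √(5.7/48) = .34 for withdrawal. After 20% dilution the first two still have about 95% and 79% power at N=60. Withdrawal starts below .37 and has no such reserve.

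A reader might also infer that a chance imbalance of other-product users between arms of about 30 is a design flaw. It is not: randomisation and the test's alpha already allow for imbalance in factors outside the urn.

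**Conclusion.** The point holds as a mismatch between target and procedure. The reviewed text aims at nicotine abstinence, but instructs and asks about cigarettes only, sets a number only for CO, and leaves its nicotine biomarkers without threshold, consequence or analysis role. The likely result is dilution toward no difference. Use that differed by arm could bias either way, but nothing in the documents points to that.

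The size cannot be fixed from the documents. Power of 76% to 62%, against about 80% planned, rests on an assumed 5% to 20% of women showing no drug effect, and is an upper limit on the harm for those shares. The documents do not support the inference that such women would be out of withdrawal altogether, or that they would be certified abstinent on every test. This should be corrected because the remedy is cheap; it does not invalidate the design.

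**What to change.** 1. **Protocol 5.E, abstinence sessions:** ask women to refrain from cigarettes and all other nicotine products from the evening of Medication Day 5.
2. **Protocol 5.E, check-in visits:** extend the self-report on Days 6 and 7 to any nicotine product, and ask it again on Day 8.
3. **Protocol 5.B (Biochemical) and SAP:** pre-specify how Day 8 plasma nicotine and the baseline-to-Day-8 fall in plasma cotinine define nicotine abstinence. Plasma nicotine mainly reflects recent use (general knowledge), so it should be read together with the cotinine fall and the self-report. The order of procedures in 5.E already places the blood draw before the Smoking Choice Paradigm.
4. **SAP:** use that definition in a sensitivity analysis beside the ANCOVA in all randomised women. It should not replace that analysis, because abstinence is observed after randomisation and may itself depend on treatment.
5. **Housekeeping:** reconcile the CO rule, which is 8 ppm or below in 5.B but below 8 ppm in the Payment section.

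Excluding current users of other products is optional and would cost recruitment. The rest needs amendment wording, one self-report item and one further analysis, with no new assay or visit.
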